7.2.2. Graded Laboratory Values

The Gilead Grading Scale for Severity of Adverse Events and Laboratory Abnormalities will be used for assigning toxicity grades to laboratory results for analysis as Grade 0, Grade 1, Grade 2, Grade 3, or Grade 4. Grade 0 includes all values that do not meet the criteria for an abnormality of at least Grade 1. Some laboratory tests have criteria for both increased and decreased levels; analyses for each direction (ie, increased, decreased) will be presented separately.

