4.3. Exclusion Criteria

Subjects who meet *any* of the following exclusion criteria are not to be enrolled in this study.

- 1) Pregnant or lactating subjects
- 2) Sexually-active males or females of childbearing potential who are not willing to use an effective method of contraception during the study (see [Appendix 5](#) for further details)
- 3) Treatment-naïve subjects with GT-3 HCV infection as determined at Screening. Treatment naïve is defined by no prior exposure to any IFN, RBV, or other approved or experimental HCV-specific DAA agent
- 4) Decompensated liver disease defined as INR $>$ 1.2 \times ULN, platelets $<$ 50,000/mm³, serum albumin $<$ 3.5 g/dL, or prior history of clinical hepatic decompensation (e.g., ascites, jaundice, encephalopathy, variceal hemorrhage)
- 5) Chronic liver disease of a non-HCV etiology (e.g., hemochromatosis, Wilson's disease, alpha-1 antitrypsin deficiency)

- 6) α -fetoprotein > 50 ng/mL
- 7) Serum creatinine > 1.5 mg/dL
- 8) Estimated glomerular filtration rate < 90 mL/min/1.73m², as calculated by the Schwartz Formula
- 9) Evidence of hepatocellular carcinoma (HCC) or other malignancy (with the exception of certain resolved skin cancers)
- 10) Co-infection with HIV, acute HAV, or HBV (i.e. Hepatitis B Surface Ag positive at screening)
- 11) Significant cardiovascular, pulmonary, or neurological disease
- 12) Evidence of a gastrointestinal malabsorption syndrome that may interfere with absorption of orally administered medications
- 13) History of solid organ or bone marrow transplantation
- 14) Chronic daily non-steroidal anti-inflammatory drug therapy
- 15) Systemic corticosteroid use for > 2 weeks (pulmonary/nasal administration is permitted)
- 16) Investigational agents taken within the past 28 days (except with the expressed approval of the Sponsor)
- 17) Clinically-relevant alcohol or drug abuse within 12 months of screening. A positive drug screen will exclude subjects unless it can be explained by a prescribed medication; the diagnosis and prescription must be approved by the investigator
- 18) Known hypersensitivity to the study drug, the metabolites, or formulation excipients
- 19) Any other condition (including alcohol or substance abuse) or prior therapy that, in the opinion of the Investigator, would make the subject unsuitable for the study or unable to comply with dosing requirements
- 20) Use of any prohibited concomitant medications as described in Section 5.6

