6.6. Procedures and Specifications

6.6.1. Clinical Laboratory Analytes

Hematology: Hematocrit, Hemoglobin (Hb), Platelet count, Red blood cell count (RBC), White blood cell count (WBC) with differential (absolute and percentage) including Lymphocytes, Monocytes, Neutrophils, Eosinophils, Basophils, Reticulocyte count and MCV.

Coagulation: INR, Prothrombin time (PT), Activated partial thromboplastin time (APTT)

Chemistry Alanine aminotransferase (ALT/SGPT), Aspartate aminotransferase (AST/SGOT), Albumin, Alkaline phosphatase, Creatinine, Total Bilirubin (reflex to Direct Bilirubin), Glucose, Lipase, Potassium, Sodium, Gamma-glutamyl transferase (GGT), alpha fetoprotein (AFP), alpha-1 anti-trypsin, creatine kinase (CK) and amylase.

Urinalysis: Appearance, Blood, Color, Glucose, Leukocyte esterase, pH, Protein, Urobilinogen. Reflex to microscopic urinalysis if dipstick result is abnormal.

Virological Tests: Serologies for HCV and HBV (HBsAg, HBsAb, HBcAb) and HAV; serology for HIV (including reflex testing as necessary). HCV RNA will be measured using the COBAS[®] AmpliPrep/COBAS[®] TaqMan[®] HCV Test, v2.0 for Use with the High Pure System. HCV GT and subtype will be determined using the Siemens VERSANT[®] HCV Genotype INNO-LiPA 2.0 Assay. Gilead reserves the right to use alternate assays for HCV RNA and HCV GT should the above assays become unavailable.

IL28B genotype will be determined by polymerase chain reaction (PCR) amplification of the SNP, rs12979860, with sequence specific forward and reverse primers and allele specific fluorescently labeled TaqMan[®] MGB probes. Gilead reserves the rights to use alternate assays for IL28B determination should the above assay become unavailable.

Pregnancy Tests: Serum β -hCG, Urine β -hCG (if positive, requires immediate confirmation with Serum β -hCG)

Additional Tests: Urine Drug Screen (for amphetamines, cocaine, methadone, opiates), Hemoglobin A1c (HbA1c), TSH (reflex Free T4), Alfa fetoprotein (AFP), Alpha-1 anti-trypsin (AAT).

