Appendix 3. GSI Grading Scale for Severity of Adverse Events and Laboratory Abnormalities

Antiviral Toxicity Grading Scale Version: 01 April 2015

HEMATOLOGY				
	Grade 1	Grade 2	Grade 3	Grade 4
Hemoglobin				
HIV POSITIVE	8.5 to 10.0 g/dL	7.5 to < 8.5 g/dL	6.5 to < 7.5 g/dL	< 6.5 g/dL
Adult and Pediatric ≥ 57 Days	85 to 100 g/L	75 to < 85 g/L	65 to < 75 g/L	< 65 g/L
HIV NEGATIVE	10.0 to 10.9 g/dL	9.0 to < 10.0 g/dL	7.0 to < 9.0 g/dL	< 7.0 g/dL
Adult and Pediatric ≥ 57 Days	100 to 109 g/L	90 to < 100 g/L	70 to < 90 g/L	< 70 g/L
	OR	OR	OR	
	Any decrease from Baseline	Any decrease from Baseline	Any decrease from Baseline	
	2.5 to < 3.5 g/dL	3.5 to < 4.5 g/dL	≥ 4.5 g/dL	
	25 to < 35 g/L	35 to < 45 g/L	≥ 45 g/L	
Infant, 36–56 Days (HIV POSITIVE OR NEGATIVE)	8.5 to 9.4 g/dL	7.0 to < 8.5 g/dL	6.0 to < 7.0 g/dL	< 6.0 g/dL
	85 to 94 g/L	70 to < 85 g/L	60 to < 70 g/L	< 60 g/L
Infant, 22–35 Days (HIV POSITIVE OR NEGATIVE)	9.5 to 10.5 g/dL	8.0 to < 9.5 g/dL	7.0 to < 8.0 g/dL	< 7.0 g/dL
	95 to 105 g/L	80 to < 95 g/L	70 to < 80 g/L	< 70 g/L
Infant, 1–21 Days (HIV POSITIVE OR NEGATIVE)	12.0 to 13.0 g/dL	10.0 to < 12.0 g/dL	9.0 to < 10.0 g/dL	< 9.0 g/dL
	120 to 130 g/L	100 to < 120 g/L	90 to < 100 g/L	< 90 g/L
Absolute Neutrophil Count (ANC)				
Adult and Pediatric, ≥ 7 Months#	1000 to 1300/mm ³	750 to < 1000/mm ³	500 to < 750/mm ³	< 500/mm ³
	1.00 to 1.30 GI/L	0.75 to < 1.00 GI/L	0.50 to < 0.75 GI/L	< 0.50 GI/L
Absolute CD4+ Count				
HIV NEGATIVE ONLY				
Adult and Pediatric > 13 Years	300 to 400/mm ³	200 to < 300/mm ³	100 to < 200/mm ³	< 100/mm ³
	300 to 400/μL	200 to < 300/μL	100 to < 200/μL	< 100/μL

HEMATOLOGY				
	Grade 1	Grade 2	Grade 3	Grade 4
Absolute Lymphocyte Count HIV NEGATIVE ONLY Adult and Pediatric > 13 Years	600 to 650/mm ³ 0.60 to 0.65 GI/L	500 to < 600/mm ³ 0.50 to < 0.60 GI/L	350 to < 500/mm ³ 0.35 to < 0.50 GI/L	< 350/mm ³ < 0.35 GI/L
Platelets	100,000 to < 125,000/mm ³ 100 to < 125 GI/L	50,000 to < 100,000/mm ³ 50 to < 100 GI/L	25,000 to < 50,000/mm ³ 25 to < 50 GI/L	< 25,000/mm ³ < 25 GI/L
WBCs	2000/mm ³ to 2500/mm ³ 2.00 GI/L to 2.50 GI/L	1,500 to < 2,000/mm ³ 1.50 to < 2.00 GI/L	1000 to < 1,500/mm ³ 1.00 to < 1.50 GI/L	< 1000/mm ³ < 1.00 GI/L
Hypofibrinogenemia	100 to 200 mg/dL 1.00 to 2.00 g/L	75 to < 100 mg/dL 0.75 to < 1.00 g/L	50 to < 75 mg/dL 0.50 to < 0.75 g/L	< 50 mg/dL < 0.50 g/L
Hyperfibrinogenemia	> ULN to 600 mg/dL > ULN to 6.0 g/L	> 600 mg/dL > 6.0 g/L	— —	— —

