Alkaline Phosphatase	1.25 to 2.50 × ULN	> 2.50 to 5.00 × ULN	> 5.00 to 10.00 × ULN	> 10.00 × ULN
Total Amylase	> 1.0 to 1.5 × ULN	> 1.5 to 2.0 × ULN	> 2.0 to 5.0 × ULN	> 5.0 × ULN
Pancreatic Amylase	> 1.0 to 1.5 × ULN	> 1.5 to 2.0 × ULN	> 2.0 to 5.0 × ULN	> 5.0 × ULN
Lipase	> 1.0 to 1.5 × ULN	> 1.5 to 3.0 × ULN	> 3.0 to 5.0 × ULN	> 5.0 × ULN
Albumin Pediatrics <16 years	-	2.0 to < LLN g/dL 20 to < LLN g/L	< 2.0 g/dL < 20 g/L	NA
≥ 16 years	3.0 g/dL to < LLN 30 g/L to < LLN	2.0 to < 3.0 g/dL 20 to < 30 g/L	< 2.0 g/dL < 20 g/L	NA

URINALYSIS				
	Grade 1	Grade 2	Grade 3	Grade 4
Hematuria (Dipstick)	1+	2+	3-4+	NA
Hematuria (Quantitative) See Note below				
Females	>ULN - 10 RBC/HPF	> 10-75 RBC/HPF	> 75 RBC/HPF	NA
Males	6-10 RBC/HPF	> 10-75 RBC/HPF	> 75 RBC/HPF	NA
Proteinuria (Dipstick)	1+	2-3+	4+	NA
Proteinuria, 24 Hour Collection				
Adult and Pediatric ≥ 10 Years	200 to 999 mg/24 h	>999 to 1999 mg/24 h	>1999 to 3500 mg/24 h	> 3500 mg/24 h
Pediatric > 3 Mo to < 10 Years	201 to 499 mg/m ² /24 h	>499 to 799 mg/m ² /24 h	>799 to 1000 mg/m ² /24 h	> 1000 mg/ m ² /24 h
Glycosuria (Dipstick)	1+	2-3+	4+	NA

Notes:

- Toxicity grades for Quantitative and Dipstick Hematuria will be assigned by Covance Laboratory, however for other laboratories, toxicity grades will only be assigned to Dipstick Hematuria.
- With the exception of lipid tests, any graded laboratory test with a result that is between the LLN and ULN should be assigned Grade 0.
- If the severity of a clinical AE could fall under either one of two grades (e.g., the severity of an AE could be either Grade 2 or Grade 3), select the higher of the two grades for the AE.

CARDIOVASCULAR				
	Grade 1	Grade 2	Grade 3	Grade 4
Cardiac Arrhythmia (general) (By ECG or physical exam)	Asymptomatic AND No intervention indicated	Asymptomatic AND Non-urgent medical intervention indicated	Symptomatic, non-life-threatening AND Non-urgent medical intervention indicated	Life-threatening arrhythmia OR Urgent intervention indicated
Cardiac-ischemia/Infarction	NA	NA	Symptomatic ischemia (stable angina) OR Testing consistent with ischemia	Unstable angina OR Acute myocardial infarction
Hemorrhage (significant acute blood loss)	NA	Symptomatic AND No transfusion indicated	Symptomatic AND Transfusion of ≤ 2 units packed RBCs (for children ≤ 10 cc/kg) indicated	Life-threatening hypotension OR Transfusion of > 2 units packed RBCs indicated (for children ≤ 10 cc/kg) indicated

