3.2. Subject Grouping

For analyses based on the All Enrolled Analysis Set or FAS, subjects will be grouped according to the treatment to which they were enrolled. For analyses based on the Safety Analysis Set, subjects will be grouped according to the actual treatment received. The actual treatment received is defined as the enrolled treatment except for subjects who received treatment that differs from the enrolled treatment for the entire treatment duration. In this case, the actual treatment received is defined as the treatment received for the entire treatment duration.

Generally, subjects are analyzed, except for the safety analysis, by treatment groups based on age group, HCV genotype, prior treatment experience, cirrhosis status, and treatment duration:

Table 3-1. Non-safety Treatment Groups*

12 to < 18 Years Old		3 to < 12 Years Old			
LDV/SOF (90/400 mg) 12 Weeks		LDV/SOF (45/200 mg or 33.75/150 mg) 12 Weeks		LDV/SOF (45/200 mg) 24 Weeks	LDV/SOF+RBV (45/200 mg) 24 Weeks
GT1 TN w/ or w/o cirrhosis (N =)	GT1 TE without cirrhosis (N =)	GT1, GT4 TN w/ or w/o cirrhosis (N =)	GT1 TE without cirrhosis (N =)	GT1 TE with cirrhosis (N =)	GT3 TE w/ or w/o cirrhosis (N =)
6 to < 12 Years Old			3 to < 6 Years Old		
LDV/SOF (45/200 mg) 12 Weeks		LDV/SOF (45/200 mg) 24 Weeks	LDV/SOF+RBV (45/200 mg) 24Weeks	LDV/SOF (45/200 mg or 33.75/150 mg) 12 Weeks	
GT1, GT4 TN w/ or w/o cirrhosis (N =)	GT1 TE without cirrhosis (N =)	GT1 TE with cirrhosis (N =)	GT3 TE w/ or w/o cirrhosis (N =)	GT1, GT4 TN w/ or w/o cirrhosis (N =)	

GT = genotype, TN = Treatment Naïve, TE = Treatment Experienced, w/ = with, w/o = without
 *Treatment Groups reflect the subjects actually enrolled.

For the safety analysis, subjects will be analyzed by the following groups based on age group, treatment regimen and duration:

Table 3-2. Safety Treatment Groups

12 to < 18 Years Old	3 to < 12 Years Old		
LDV/SOF (90/400 mg) 12 Weeks (N =)	LDV/SOF (45/200 mg or 33.75/150 mg) 12 Weeks (N =)	LDV/SOF (45/200 mg) 24 Weeks (N =)	LDV/SOF+RBV (45/200 mg) 24 Weeks (N =)
6 to < 12 Years Old			3 to < 6 Years Old
LDV/SOF (45/200 mg) 12 Weeks (N =)	LDV/SOF (45/200 mg) 24 Weeks (N =)	LDV/SOF+RBV (45/200 mg) 24 Weeks (N =)	LDV/SOF (45/200 mg or 33.75/150 mg) 12 Weeks (N =)

Subjects in the 3 to < 6 years of age group will have additional selected efficacy and safety analyses performed according to baseline weight in the following subgroups:

Table 3-3. Subgroups for Selected Analyses in 3 to < 6 years of Age

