7.2.2.2. Summaries of Laboratory Abnormalities

Laboratory data that are categorical will be summarized using the number and percentage of subjects in the study with the given response at baseline and each scheduled postbaseline visit.

The following summaries (number and percentage of subjects) for treatment-emergent laboratory abnormalities will be provided by analyte and treatment group; subjects will be categorized according to the most severe postbaseline abnormality grade for a given analyte:

- Graded laboratory abnormalities
- Grade 3 or above laboratory abnormalities

For all summaries of laboratory abnormalities, the denominator is the number of subjects with nonmissing postbaseline values up to 30 days after last dose for the laboratory parameter of interest.

A by-subject listing of treatment-emergent Grade 3 or above laboratory abnormalities will be provided by subject ID number and visit in chronological order. This listing will include all test results that were collected throughout the study for the analyte of interest, with all applicable severity grades or abnormal flags displayed.

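### Graded lymphocyte rows: children under 12 have no grading criterion but count as Grade 0 in the denominator, so their entry is 0/N whatever the counts

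*SAP*

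**What the plan says.** The severity scale in Protocol Appendix 3 has one lymphocyte row, headed "Absolute Lymphocyte Count HIV NEGATIVE ONLY Adult and Pediatric > 13 Years". No row covers younger children. The neutrophil row in the same table is headed "Adult and Pediatric, ≥ 7 Months", so it covers every enrolled age, and the WBC and platelet rows carry no age limit.

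HIV-positive children cannot enter: Protocol 4.3 lists "Co-infection with HIV, acute HAV, or HBV" among the exclusions. Lymphocytes are part of the hematology panel in Protocol 6.6.1: "White blood cell count (WBC) with differential (absolute and percentage) including Lymphocytes, Monocytes, Neutrophils, Eosinophils, Basophils, Reticulocyte count and MCV". Protocol Appendix 2 schedules hematology at every Treatment Phase visit and at post-treatment Weeks 4 and 12.

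SAP 7.2.2 adopts the Gilead scale and adds that "Grade 0 includes all values that do not meet the criteria for an abnormality of at least Grade 1". SAP 7.2.2.1 calls an abnormality treatment-emergent when the grade rises by at least one from baseline. If baseline is missing, any value of Grade 1 or higher counts. SAP 7.2.2.2 says that for all laboratory abnormality summaries "the denominator is the number of subjects with nonmissing postbaseline values up to 30 days after last dose for the laboratory parameter of interest".

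On columns, SAP 3.2 states: "For the safety analysis, subjects will be analyzed by the following groups based on age group, treatment regimen and duration". Table 3-2 shows LDV/SOF+RBV only for 6 to <12 years, and the pooled 3 to <12 block repeats that column. The note to the LDV/SOF dosing table in SAP 4.2.2 confirms that nobody aged 12 to <18 or 3 to <6 was assigned 24 weeks.

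**The concern.** A child with no applicable criterion can never meet Grade 1, so the rule makes that child Grade 0 at baseline and at every later visit. The child still counts in the denominator. The table then sets columns in which no lymphocyte event can be registered beside an adolescent column in which events can be registered for part of the group. For this analyte, the difference between columns reflects which ages the scale covers and says nothing about the drug.

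The primary objective of the Treatment Phase is safety and tolerability, and graded abnormalities by age group and regimen are among its standard displays. A 0/N entry in the younger columns would be read as an observed absence of events, when the row carries no information there.

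**Working it through.** The plan states no figure for this point that could be reproduced, so the check traces the rules and then sizes the effect. It assumes that the scale named in the SAP is the version in Protocol Appendix 3.

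**1. Applicable criterion.** HIV co-infection is excluded, so the HIV-negative row is the only candidate, and it starts above 13 years. Subjects aged 3 to <12 at first dose have no criterion.

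**2. Could a child age into the row?** Take a child dosed the day before turning 12, treated for the planned duration plus the 3-day visit window, and followed for 30 days. Oldest age = 12 + (treatment days + 3 + 30)/365.25.
- 12 weeks: 12 + (84 + 33)/365.25 = 12.32 years
- 24 weeks: 12 + (168 + 33)/365.25 = 12.55 years

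Both are well below 13, so ageing does not help.

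**3. Numerator.** With every value at Grade 0, no rise of one grade is possible. The missing-baseline rule also needs a value of at least Grade 1. The numerator is therefore 0 for any set of counts.

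**4. Denominator.** It requires a nonmissing postbaseline value and does not require that the value can be graded. With hematology drawn at every on-treatment visit, nearly every child qualifies.

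**5. Result for 3 to <12 years.** The entries are 0/N in each column and about 0/120 over the age group. A reader could attach an exact two-sided 95% upper limit of 1 − 0.025^(1/120) = 3.0% to that, although the row cannot support any limit. The documents give no lymphopenia rate. For a range of assumed true rates in 120 children:

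| Assumed true rate | Expected children affected | Chance of at least one | Table shows |
|---|---|---|---|
| 1% | 1.2 | 70% | 0 |
| 2% | 2.4 | 91% | 0 |
| 5% | 6 | 99.8% | 0 |
| 10% | 12 | >99.9% | 0 |

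**6. Result for 12 to <18 years.** Assume ages are evenly spread over six years. If the limit means older than 13.0, 1/6 of the group cannot be graded. If it means completed years of 14 and over, 2/6 = 1/3 cannot. Displayed rate = true rate × (1 − share not gradable), that is, 5/6 to 2/3 of the true rate. An assumed 6%, chosen only for illustration, would appear as 5% to 4%.

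**7. Scale against SAP.** The scale's own note is narrower than the SAP rule: it says "any graded laboratory test with a result that is between the LLN and ULN should be assigned Grade 0". The SAP rule takes in every value that meets no criterion, so a lymphocyte count below the reference range in a young child also becomes Grade 0.

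**The case against.** The strongest reply is that nothing is hidden. SAP 7.2.1 summarizes lymphocytes by treatment group and window, including the minimum and change from baseline, with median plots. SAP 7.2 flags out-of-range values in the by-subject listings whether or not they are graded. A clinically important fall can be reported as an adverse event. WBC and neutrophils are graded at all enrolled ages. All of this stands. A reader might infer that low lymphocyte counts in children under 12 cannot be seen or counted at all, and the documents do not support that. None of these displays, however, corrects a misleading 0% in the graded row.

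A second reply is that the SAP does not expressly address values for which the scale has no criterion, so a programmer might leave them ungraded. That is a possible reading, and the scale's narrower note on Grade 0 lends it some support. But the SAP sentence covers all values that do not meet Grade 1, and the denominator rule would keep those children in either case.

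A third reply is that the consequence is small, and that is fair. The primary safety endpoint in Protocol 9.1.2 is an adverse event leading to permanent discontinuation of study drug. Laboratory data have no inferential analysis, and Grade 1 begins only at 650/mm³, so few events are likely. A reader might also infer that a ribavirin effect is being masked. The documents do not support that: Protocol 1.2.1 links added ribavirin to anemia and raised bilirubin, and both are graded at every enrolled age.

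**Conclusion.** The point holds for a limited set of outputs: the lymphocyte row of the graded treatment-emergent tables (all grades, and Grade 3 or above) and the listing of treatment-emergent Grade 3 or above abnormalities. There, the rules as written give an uninformative zero for the whole 3 to <12 group, about 120 of 220 planned subjects, and for every ribavirin-treated child. That result is certain once the Appendix 3 scale and the SAP text are applied. The dilution of the adolescent column, by 1/6 to 1/3, depends on an even spread of ages. The rates used to illustrate size are assumptions.

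This is a stated rule that yields a wrong incidence, so it merits correction. It is not evidence of a safety signal, and the underlying lymphocyte data are not lost.

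**What to change.** Add to SAP 7.2.2 and 7.2.2.2 wording to this effect: *Where the grading scale gives criteria only for a stated age range (for example, absolute lymphocyte count, over 13 years), values from subjects outside that range are not graded and are not set to Grade 0. Those subjects are excluded from numerator and denominator for that analyte, and the number not gradable is displayed.* The same text should say whether the limit is read in decimal age or completed years.

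The 3 to <12 columns would then have a graded-lymphocyte denominator of 0 and be shown as not graded. The 12 to <18 percentage would be based only on subjects who can be graded. The cost is a few sentences and one displayed count, with no new data.

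Optionally, add by age group and regimen the number of subjects whose lymphocyte count moves from normal at baseline to below the laboratory's lower limit of normal, using the reference-range flags already planned in SAP 7.2. The downside is that this count includes mild decreases and cannot be compared with the graded rows, so it should be labelled separately.

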7.2.2.1. Treatment-Emergent Laboratory Abnormalities

Treatment-emergent laboratory abnormalities are defined as values that increase at least 1 toxicity grade from baseline at any postbaseline time point, up to and including the date of last dose of study drug plus 30 days for subjects who permanently discontinued study drug, or all available data in the database snapshot for subjects who were still on treatment at the time of an interim analysis. If the relevant baseline laboratory value is missing, then any abnormality of at least Grade 1 will be considered treatment emergent.

7.2.2.2. Summaries of Laboratory Abnormalities

Laboratory data that are categorical will be summarized using the number and percentage of subjects in the study with the given response at baseline and each scheduled postbaseline visit.

The following summaries (number and percentage of subjects) for treatment-emergent laboratory abnormalities will be provided by analyte and treatment group; subjects will be categorized according to the most severe postbaseline abnormality grade for a given analyte:

- Graded laboratory abnormalities
- Grade 3 or above laboratory abnormalities

For all summaries of laboratory abnormalities, the denominator is the number of subjects with nonmissing postbaseline values up to 30 days after last dose for the laboratory parameter of interest.

A by-subject listing of treatment-emergent Grade 3 or above laboratory abnormalities will be provided by subject ID number and visit in chronological order. This listing will include all test results that were collected throughout the study for the analyte of interest, with all applicable severity grades or abnormal flags displayed.

7.2.2.3. On-Treatment Liver-Related Laboratory Events

The following liver-related laboratory events will be summarized using data from all the on-treatment postbaseline visits (up to 2 days after the last dose of any study drug):

- Aspartate aminotransferase (AST) or ALT $> 3 \times$ ULN and total bilirubin $> 2 \times$ ULN
- ALT $> 5 \times$ ULN
- Total bilirubin $> 2 \times$ ULN

For the composite criterion of AST or ALT and total bilirubin, AST or ALT and total bilirubin must meet the specified cut-offs at a given postbaseline time point; subjects will be counted once when the criterion is met. The denominator will be the number of subjects in the Safety Analysis Set with at least 1 postbaseline value of AST or ALT and total bilirubin at the same time point. For individual laboratory tests, subjects will be counted once based on the most severe postbaseline values when the criterion is met. The denominator will be the number of subjects in the Safety Analysis Set with at least 1 nonmissing postbaseline value for the test. A listing will be provided including ALT, AST, total bilirubin, direct bilirubin, alkaline phosphatase, HCV RNA (\log_{10}) and yes/no flag for subjects meeting at least 1 of the 3 criteria. All the available data for the subjects will be listed.

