7.2. Subject Stopping Rules for LDV/SOF FDC and RBV

The Gilead Medical Monitor should be consulted prior to dose discontinuation of LDV/SOF FDC unless the investigator believes that immediate action is warranted to ensure the continued safety of the subject.

Administration of LDV/SOF FDC may be discontinued due to a clinical or laboratory event. There is no option for LDV/SOF FDC dose reduction. If LDV/SOF FDC is stopped for toxicity, it should not be restarted, RBV should be stopped (GT-3 subjects only), and the subject should complete an Early Termination Visit.

Subjects who meet any of the following laboratory criteria must stop treatment with LDV/SOF FDC:

- Elevation of ALT and/or AST >5× Day 1 or nadir, confirmed by immediate repeat testing
- Abnormal elevation of ALT >3× Day 1 and total bilirubin >2 × ULN, confirmed by immediate repeat testing
- Confirmed elevation of ALT >15 × ULN, confirmed by immediate repeat testing
- Any Grade 3 or greater rash associated with constitutional symptoms
- Any Grade 4 event or lab abnormality assessed as related to treatment with LDV/SOF FDC

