9.5. Safety Analysis

Safety analysis will be performed for PK Lead-in Phase and for Treatment Phase respectively. Safety data will be summarized by age group and overall for PK Lead-in Phase and by treatment regimen for each age group for the Treatment Phase.

Safety will be evaluated by assessment of clinical laboratory tests, physical examinations, vital signs measurements, and by the documentation of AEs.

All safety data collected while on or after the first dose of study drug administration up to 30 days after the last dose of study drug will be summarized according to the study drug received.

Safety endpoints will be analyzed by the number and percent of subjects with events or abnormalities for categorical values or 8-number summary (n, mean, standard deviation, median, Q1, Q3, minimum, maximum) for continuous data.

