3.7.2. Analysis Windows

Subject visits might not occur on protocol-specified days. Therefore, for the purpose of analysis, observations will be assigned to analysis windows.

In general, the baseline value will be the last nonmissing value on or prior to the first dose date of study drug.

HCV RNA, vital signs, and safety laboratory data collected up to the last dose date + 2 days are considered to be on-treatment data and HCV RNA, vital signs and safety laboratory data collected after the last dose date + 2 days are considered posttreatment data. The analysis windows for on-treatment HCV RNA, vital signs and safety laboratory data are provided in [Table 3-4](#).

Table 3-4. Analysis Windows for On-treatment HCV RNA, Vital Signs and Safety Laboratory Data

Nominal Visit	LDV/SOF FDC 12 Weeks			LDV/SOF FDC ± RBV 24 Weeks		
	Nominal Day	Lower Limit	Upper Limit	Nominal Day	Lower Limit	Upper Limit
Baseline	1	(none)	1	1	(none)	1
Week 1	7	2	11	7	2	11
Week 2	14	12	21	14	12	21
Week 4	28	22	42	28	22	42
Week 8	56	43	70	56	43	70
Week 12	84	71	≥ 85	84	71	98
Week 16	NA			112	99	126
Week 20				140	127	154
Week 24				168	155	≥ 169

Subjects who participated in the PK Lead-in Phase will immediately roll over into the Treatment Phase with no interruption of study drug administration until the appropriateness of the dose is confirmed by PK and safety data from the PK-Lead-in Phase. These subjects will start at the Week 2 visit of the Treatment Phase. Week 1 records for these subjects will be chosen from Day 10 in the PK Lead-in Phase.

HCV RNA, vital sign, and safety laboratory data collected after the last dose date + 2 days will be assigned to the posttreatment follow-up (FU) visits. Visit windows will be calculated from the last dose date (ie, FU Day = collection date minus the last dose date) as shown in [Table 3-5](#).

Table 3-5. Analysis Windows for Posttreatment HCV RNA, Body Weight, Height, Vital Sign and Safety Laboratory Data

Nominal FU ^a Visit	HCV RNA, Body weight and Height			Vital Signs and Safety Laboratory Data ^b		
	Nominal FU Day	Lower Limit	Upper Limit	Nominal FU Day	Lower Limit	Upper Limit
FU-4	28	21	69	28	3	30
FU-12	84	70	146	NA	NA	NA
FU-24	168	147	210	NA	NA	NA

a FU-x visit = posttreatment Week-x follow-up visit.

b Vital signs (blood pressure, pulse, respiratory rate, and temperature) and safety labs will only be summarized for the FU-4 visit (up to 30 days after last dose).

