7.10. Changes From Protocol-Specified Safety Analyses

There are no deviations from the protocol-specified safety analyses.

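### The SAP's only joint AST/ALT-and-bilirubin count ends 2 days after the last dose, so a joint rise first met on Days 3 to 30 is not counted as a joint event

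*SAP*

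**What the plan says.** SAP 7.2.2.3 summarises three liver-related criteria: AST or ALT > 3 × ULN with total bilirubin > 2 × ULN; ALT > 5 × ULN; and total bilirubin > 2 × ULN. It does this "using data from all the on-treatment postbaseline visits (up to 2 days after the last dose of any study drug". For the composite, "AST or ALT and total bilirubin must meet the specified cut-offs at a given postbaseline time point". The accompanying listing carries a "yes/no flag for subjects meeting at least 1 of the 3 criteria. All the available data for the subjects will be listed".

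The 2-day limit follows the SAP's general rule in 3.7.2, under which "safety laboratory data collected up to the last dose date + 2 days are considered to be on-treatment data". Later laboratory values go to the FU-4 visit, which Table 3-5 runs from Day 3 to Day 30.

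The other safety summaries reach 30 days. SAP 7.2.2.1 defines treatment-emergent laboratory abnormalities "up to and including the date of last dose of study drug plus 30 days for subjects who permanently discontinued study drug", and SAP 7.2.2.2 tabulates them one analyte at a time. SAP 7.1.5.1 uses 30 days for adverse events. Protocol 9.5 says that safety data "up to 30 days after the last dose of study drug will be summarized according to the study drug received".

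Protocol 7.2 states: "Subjects who meet any of the following laboratory criteria must stop treatment with LDV/SOF FDC". One trigger is a confirmed ALT and/or AST rise above 5 × Day 1 or nadir, with no bilirubin condition. SAP 7.10 states: "There are no deviations from the protocol-specified safety analyses".

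**The concern.** Safety and tolerability are the primary objective of the Treatment Phase. A transaminase rise and a bilirubin rise in the same child at the same time carry information that two separate rows of graded results do not, and only SAP 7.2.2.3 looks for the combination.

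When a child stops drug on a transaminase rise alone, the table's 2-day clock starts while bilirubin may still be changing. If bilirubin first passes 2 × ULN on Day 3 or later, the child is outside the composite row. A reader who meets a zero there could take it to cover the 30-day safety window used elsewhere, when it covers treatment plus 2 days.

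**Working it through.** This is mainly a comparison of text, with two small calculations.

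**1. Windows side by side**

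| Summary | Ends at | Joint criterion? |
|---|---|---|
| SAP 7.2.2.3, liver events | last dose + 2 days | yes |
| SAP 7.2.2.1 and 7.2.2.2, graded laboratory values | last dose + 30 days | no, by analyte |
| SAP 7.1.5.1, treatment-emergent AEs | last dose + 30 days | no |
| Protocol 9.5, safety data generally | last dose + 30 days | none specified |

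No summary combines a joint criterion with Days 3 to 30.

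**2. Which draws fall in the gap**

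Chemistry is drawn at post-treatment Weeks 4 and 12, each ± 5 days (Protocol 6.5.1 and 6.5.2).

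- Week 4: 28 − 5 = 23 to 28 + 5 = 33, so 33 − 23 + 1 = 11 permitted days. On or before Day 2: 0. From Day 23 to Day 30: 30 − 23 + 1 = 8. Days 31 to 33: 3.
- Week 12: 84 − 5 = 79 to 84 + 5 = 89. This is outside both limits.
- Early Termination: chemistry is drawn (Protocol 6.4.9), but neither 3.5 nor 6.4.9 sets a deadline relative to the last dose. A draw on Day 3 or later is outside the liver table.

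**3. Whether the liver listing closes the gap**

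The stop trigger relative to nadir, in multiples of ULN, is 5 × nadir. The documents give no nadir values, so these are assumptions:

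- nadir 0.4 × ULN: 5 × 0.4 = 2.0 × ULN
- nadir 0.5 × ULN: 5 × 0.5 = 2.5 × ULN
- nadir 0.8 × ULN: 5 × 0.8 = 4.0 × ULN

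Any nadir below 1.0 × ULN puts the trigger below the ALT > 5 × ULN criterion. An AST-only stop meets no single-test criterion, because the table has none for AST. If the listing shares the table's window, such a child whose bilirubin rises from Day 3 onward is neither counted as a joint event nor listed there. By contrast, a stop for ALT > 15 × ULN meets the ALT > 5 × ULN criterion, and the ALT-plus-bilirubin stop meets the bilirubin criterion. If those values fall inside the window, the child is listed with all available data.

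**4. Whether the Grade 3+ listing closes the gap**

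In Protocol Appendix 3, Grade 2 is > 2.5 to 5.0 × ULN for ALT and AST and > 1.5 to 2.5 × ULN for bilirubin. A joint event with ALT or AST above 3 and up to 5 × ULN and bilirubin above 2 and up to 2.5 × ULN is therefore Grade 2 on both analytes. On Days 3 to 30 it does not by itself enter the listing of Grade 3 or above in SAP 7.2.2.2.

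**The case against.** The case against is substantial, and most of it stands.

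- **The child who stops is captured elsewhere.** Protocol 8.1.3 requires a laboratory abnormality that leads to discontinuation of study drug to be recorded as an AE. That AE counts in the Treatment Phase primary safety endpoint (Protocol 9.1.2), is treatment-emergent by definition (SAP 7.1.5.1), and is tabulated and listed (SAP 7.1.6). This stands, although the AE entry need not show that bilirubin rose as well.
- **The values are still reported.** Each analyte is graded to 30 days. SAP 7.2 also lists serum chemistry by subject and visit with abnormal values flagged, so ALT, AST and bilirubin from one visit can be read together. This stands, but a reader would have to search that listing for the joint event.
- **The limit is deliberate.** The section is titled as on-treatment and applies the definition in SAP 3.7.2 consistently. This stands. What is missing is a companion count for Days 3 to 30.
- **The listing sentence states no 2-day limit of its own.** This is fair, and the wording is open. That is why a child may be absent from the listing, not certainly so.

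A reader might infer that SAP 7.10 is contradicted. The documents do not support that. Protocol 9.5.3 asks for graded treatment-emergent abnormalities to 30 days, and the SAP delivers them. The protocol specifies no composite liver table; the SAP adds one.

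**Conclusion.** The point holds in a narrow form. A joint elevation first met on Days 3 to 30 enters no joint count. The liver listing and the Grade 3+ listing can both miss it after an AST-only stop or an ALT stop from a low nadir, when the values lie in the Grade 2 ranges above. This is a gap in a supplementary table that is cheap to close.

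A reader might go further and infer that children with liver signals leave safety reporting once they stop drug. They do not: the AE, the single-analyte grades and the raw chemistry all remain.

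On size, no permitted Week 4 draw day lies inside the 2-day limit, and 8 of 11 lie inside 30 days. The documents give no rate from which to estimate how many children would be affected. Counting excluded calendar days would mislead, because the Week 4 draw is the only scheduled post-treatment draw that can fall in that span.

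The conclusion rests on three assumptions: the listing uses the table's window, an Early Termination draw can fall on Day 3 or later, and some children have a nadir below ULN.

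**What to change.** In SAP 7.2.2.3, keep the present on-treatment rows. Add rows applying the same three criteria to all post-baseline values up to last dose plus 30 days, as in SAP 7.2.2.1, with denominators defined over the same window. State that the listing selects subjects on the 30-day window.

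The cost is a sentence or two of SAP wording and the added rows, with no new data collection and no implication for the stopping rules. There are two limits. Some late rises may reflect virologic relapse rather than drug; showing both windows, with the HCV RNA already in the listing, helps the reader judge. Week 4 draws on Days 31 to 33 would still fall outside.
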